For Objective 1, we will evaluate association of steroid dose prescribed with relapse rates, adjusting for patient characteristics. For objective 2, we will use multi-level modeling with patients nested within physicians and physicians nested within health centres, to evaluate the association of patient-, physician- and centre-related factors with variability in steroid treatment dose prescribed. An embedded qualitative study utilizing focus groups of health care providers will enrich the quantitative results by providing an understanding of attitudes, beliefs and local factors driving variation in care at participating centres, while considering provider characteristics (training background, experience) and centre characteristics (use of standardized protocols). Quantitative and qualitative results will be integrated (using a convergent parallel mixed methods design) for interpretation at the end of study, and collectively inform strategies for development and implementation of best practice treatment protocols across centres to improve overall provision of care in this patient population. *See adjacent figure for overview of study.*

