2.7 We need a collaborative research network and data infrastructure to improve outcomes in childhood nephrotic syndrome, a rare pediatric chronic disease. Childhood nephrotic syndrome is one of the most common acquired kidney diseases in children, but, it meets the Canadian Institutes for Health Research (CIHR) definition of a 'rare' disease (affects one person out of 2,000 or fewer).⁴⁹ No single centre or region in Canada has sufficient patient numbers to produce generalizable knowledge regarding effective treatments, the most significant barrier to generating high quality evidence and one that can be overcome by multi-centre collaborative studies. Clinical research networks, with the combination of high quality data and large sample size accrual, are proven powerful tools to improve health outcomes of children with rare diseases. For example, the ImproveCareNow network for pediatric inflammatory bowel disease includes 445 pediatric gastroenterologists and 50 sites, and has seen remission rates for Crohn's disease and colitis improve from 49% to 78% in just 5 years.⁵⁰⁻⁵² For steroid sensitive nephrotic syndrome in particular, there is a severe lack of well characterized clinical and/or research cohorts. There is only one single-centre cohort study in Canada documenting outcomes of steroid sensitive patients (INSIGHT study, with a focus on genetic investigations)⁵³ – creating a major gap in knowledge regarding overall quality of clinical care and patients' clinical progression and outcomes. Funding this proposal will sustain a national network, composed of >20 investigators, with an estimated 50 physicians who will enroll from 13 sites, and establish the *only* national longitudinal observational cohort study for children with nephrotic syndrome.

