The standard definitions used in nephrotic syndrome are provided in Appendix, Table 2. The data collection forms, shown in Appendix Figure 3, are designed to capture steroid prescriptions for each episode from the date of start of full dose steroid therapy (60 mg/m² or 2mg/kg) to cessation of steroid therapy or restart of full dose therapy. Each patient’s steroid prescription for an episode will be linked to the prescribing physician.

Data quality and standardization: Standardized case report forms will be used for data collection regarding the clinical course, outcomes and treatments for childhood nephrotic syndrome. All patient and physician data will be entered by study staff into a multi-centre online database (REDCap™, a web-application which allows users to build databases securely for the purposes of research and in particular for longitudinal cohort studies, <http://project-redcap.org/> hosted by Women and Children’s Research Institute, Edmonton, see letter from [name]). Data are being monitored weekly to address data quality issues in real-time. Based on the 77 subjects enrolled to date, we have confirmed that the majority of data to be collected for this study is recorded routinely by nursing staff in clinical care, and the web based system does not pose significant additional onerous data entry requirements.

The study will be coordinated centrally in Calgary. Two central study staff (study nurse and data analyst) will train all other site-specific study staff regarding study goals and objectives, data management and data entry. We put in place several measures to ensure data consistency and standardization including: piloting case report forms and standardizing forms; training site staff for data element definitions; using a data dictionary; establishing inter-rater reliability for data entry using two study staff at each site at start of study; and pre-study patient visit planning to standardize data collection and entry. Every 3 months, data analyst will review data entry completeness for individual patients and send reminders to appropriate site investigators for data completion. There will be a 2 step review for data completeness for each patient record – first by the data analyst and second by a lead investigator or designate. Data are time-stamped as complete after review. Key measures of data quality were identified a priori; a sample data quality report is attached in Appendix, Tables 3 and page 16.

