Feasible sample and power considerations: We estimated a feasible sample based on data gathered from 2 sources: an ongoing longitudinal study of children with nephrotic syndrome (INSIGHT study, led by [name]) recruiting a Toronto based cohort,⁵³ and our preliminary data (Appendix Figure 5 for preliminary recruitment rate). Based on the expected consent rate of 72%, and estimated drop out of 10% (due to loss to follow-up or steroid resistance), we estimate that we will be able to enrol and follow, at least, 520 patients over a period of 4.0 years (65 patients every 6 months). In our preliminary work, we have already enrolled 77 patients from 6 sites, thus our total estimated sample is 597 patients.

Although we hypothesize that increasing steroid dose prescribed per unit time will be associated with decreasing relapse rates, no studies to date have reported a specific magnitude of the effect of steroid prescribed per unit time on relapse rates. A systematic review of available clinical trials examining this issue, published in 2007, only reports on risk ratios based on the dichotomous outcome of any relapse at a pre-specified time interval (usually 12 or 24 months).⁴⁰ Our outcome of interest is an actual rate (count of relapses/person years). Hence, a power based, effect size dependent sample size calculation was not performed. At a significance level $\alpha = 0.05$, and under the following assumptions of a mean daily steroid dose of $30.64 \text{ mg}/\text{m}^2$ with a standard deviation (of the dose) of 8.85, a base rate of relapse of 1.68 per person year, average follow up (time at risk of relapse) of 2 years and a conservative correlation (R^2) of the steroid dose with other covariates of 0.2, we would have 90% power to detect an incidence rate

ratio of 0.989 or smaller (i.e. a larger effect size) in a multiple Poisson regression. We are allowing for a 2 tailed test to allow the possibility of the effect being on either side of the null.

3.3 Work Plan for Objective 2

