Outcomes: The primary outcome is steroid prescribed per episode. We will examine: a) total dose patients receive for an episode; and b) average daily dose by dividing the total dose by duration (in days) of the episode. Dose will always be in mg/m² prednisone equivalents. This outcome definition is consistent with measures of steroid exposure used in prior nephrotic syndrome steroid dosing studies.^{38,55} We are evaluating steroid prescription per episode because in this objective, we will study determinants of variability in steroid prescription for episodes of proteinuria rather than patient outcomes related to cumulative exposure of steroids (e.g. relapse rate). All episodes will be categorized either as first presentation or relapse. The secondary outcome will be length of episode in days.

Exposures: Exposure variables of interest are categorized into centre-, physician- and patient-level variables. Centre-level variable is defined as existence of a standardized protocol within centre for treating first presentation and relapses (information will be obtained from the site investigator as existence of centre based protocols [yes/no]). Physician-level variables are gender, year of graduation from nephrology fellowship, and location of nephrology training (Canada vs. outside Canada). These centre- and physician-level variables were shown to impact variability in practice patterns according to our published survey.²² Patient-level variables are age, gender, ethnicity, and status at entry into study (first presentation, relapse). These variables are further described in Appendix, Table 5.

Analysis plan: We will describe the primary and secondary outcomes according to each of centre-, physician- and patient-level characteristics with 95% confidence intervals. To study the associations of centre-, physician-, patient-level characteristics with the primary outcome (steroid prescribed per episode), we will use mixed effects models with fixed effects for centre (standardized protocols yes/no), physician (gender, years in practice, location of training), and patient (age, gender, ethnicity) characteristics and random effects to account for physicians clustering within centre, patients clustering

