within physician, and episodes clustering within patients. We will create separate models to examine both total dose patients receive for the episode, and average daily dose by dividing the total dose by duration (in days) of the episode. The unit of analysis will be the episode. Each episode will be categorized as either first episode or relapse at the patient level in the same model. The same methodology will be used to study the length of episode in days (secondary outcome).

Description of the embedded qualitative study: The embedded qualitative study will enrich the quantitative results by providing detail regarding attitudes, beliefs and local factors driving variation in care - fundamental to understanding the complexity of health care professional decision-making.^{57,58} Theoretically grounded in the *Ottawa Model of Research Use*,⁵⁹ we are conducting focus groups with health professionals who care for children with nephrotic syndrome to probe the reasons for variation in steroid protocols ('why do people do what they do'). Ten focus groups, one per site with 6-8 participants per group and each lasting 60 minutes, are planned. Informed consent will be obtained and participant responses will be anonymized. We are not requesting funds from CIHR for this study as we have completed 8 of these 10 focus groups; however, we have provided the interview guide and the preliminary results in the Appendix (pages 22-24) - as it is a critical component of our mixed methods design and KT plan.

Integration of quantitative and qualitative studies: We will independently analyze the qualitative and quantitative data using analyses for Objective 2 as detailed above. We will use a convergent mixed methods analytic approach to compare the results obtained in the quantitative with qualitative components (Appendix Figure 6), using matrices of the hierarchies of centre-, physician- and patient-levels and explanatory quantitative variables at each level and themes related to these same levels arising from the qualitative study (e.g., existence of standardized protocols in each centre, age and training background of the physician, patient's age and ethnicity; Appendix Table 6), asking whether two types of data are congruent or not.

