Feasible sample and power considerations: For objective 2, there is no knowledge on expected effects from the explanatory variables on the outcome. Therefore, power calculations, which are based on having a specific alternative hypothesis, are not feasible. The analysis to be performed is a mixed effects model with three random effects (physicians within centre, patients within physicians and episodes within patients), for which there is no simple analytic formula to calculate the needed sample size. The innovative method of Monte Carlo simulation based on the number of subjects potentially available still needs to have as input the expected effects from each of the explanatory variables. In the case of this linear mixed model (for primary outcome), the effect of each variable is measured by its coefficient in the regression (for fixed effects) and by the estimated variance of the random effects. As justified in Objective 1, we expect a feasible sample of 597 subjects. Given this estimated enrollment number, and that we will have a total of 8 explanatory variables plus 3 random effects (estimated as parameters in the model), we are complying with the guideline of 10 observations (at the unit of analysis level) per variable.⁶⁰ As the unit of analysis will be the episode and an estimated 70% of patients will have more than one episode during the study, it is important to note that the 597 patients will yield from 597 to 1015 observations (episode at entry plus one additional relapse). This will ensure that estimates of random effects are feasible.

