working in this area, in order to foster creativity and innovation through trans-disciplinary collaborations. The parent group will be invited to participate in this symposium and we will also use this opportunity to conduct a semi-structured group interview to elicit patient/parent priorities and ensure that these priorities align with our work plan for the future. We have applied for a CIHR planning and dissemination grant to fund this meeting.

In the final year of funding, all stakeholders (investigators, principal knowledge users, site investigators from all 13 sites, and invited experts including representation from parent/patient groups) will be invited to a face-to-face meeting to assist in the interpretation of study results. Both the quantitative and qualitative results of the study (description of cohort, clinical course including steroid exposure and use of second line agents by centre, physician and patient variables, association of variability in steroid treatment on relapse rates, results of multi-level mixed methods models showing factors significantly associated with variation in steroid treatment, and common themes regarding variation in care elicited from focus groups) will be presented. All clinical practice guideline recommendations will also be reviewed. Utilizing all this information, we will draft best practice approaches for treatment of first presentation and subsequent relapses of nephrotic syndrome acceptable to all stakeholders. We will develop an implementation plan, informed by results of Objective 2 (centre-, physician- and patient-level characteristics driving variability in care), and ensure that the comprehensive results of this study are disseminated to physicians and other relevant stakeholders within each centre.

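### Objective 2 nests patients within physicians, but each episode is linked to its own prescriber; a child with more than one prescriber does not fit the stated model

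*Protocol*

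**What the plan says.** The Overview (Section 1.0) announces a multilevel model with "patients nested within physicians and physicians nested within health centres". Section 3.3 (Analysis plan) repeats this structure as "random effects to account for physicians clustering within centre, patients clustering" "within physician, and episodes clustering within patients". The sample-size paragraph of Section 3.3 lists the three random effects as "physicians within centre, patients within physicians and episodes within patients". The unit of analysis is the episode.

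Section 3.1 (Defining an episode of treatment) sets the data linkage at a different level: each patient's "steroid prescription for an episode will be linked to the prescribing physician".

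The text addresses physician coding in two other places. In Section 3.1, patients whose physician declines to take part go into a generic unknown category. In Section 4.0, the physician level may be dropped if physicians within centres turn out homogeneous. Neither deals with a child who has more than one prescriber.

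**The concern.** Strict nesting requires all of a child's episodes to belong to one physician. A link made episode by episode allows the physician to change within a child. Once it does, the stated random-effects structure no longer describes the data, and the analyst has two ways to force it:

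- **(a) One physician per child.** A colleague's prescription is modelled with the wrong physician's covariates and random effect. Physician effects shrink toward zero, and part of the physician variance moves into the centre and residual terms.
- **(b) One unit per child and prescriber.** The prescriber is right for every episode, but one child's episodes under different prescribers are treated as coming from independent patients. Standard errors of patient characteristics come out too small.

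Physician gender, graduation year and place of training are exposures of interest in Objective 2, and the results have a stated use: "We will develop an implementation plan, informed by results of Objective 2" (Section 6.0). Understated physician effects would mislead that plan about where variation in care arises.

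**Working it through.** **Inputs from the protocol.** "an estimated 50 physicians who will enroll from 13 sites" (Section 2.7); 597 patients, 70% with more than one episode, and up to 1,015 episodes (Section 3.3); "a base rate of relapse of 1.68 per person year, average follow up (time at risk of relapse) of 2 years" (Section 3.2).

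**Reproducing the episode count.** 597 × (1 + 0.70) = 1,014.9, which rounds to the stated 1,015. It allows one further episode for 0.70 × 597 ≈ 418 children. The Section 3.2 figures imply more: 1.68 × 2 = 3.36 relapses per child, so 4.36 episodes each and 597 × 4.36 = 2,603 in all.

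**Children with more than one prescriber.** Let s be the share of later episodes prescribed by a colleague in the same centre. The protocol gives no value; 10% to 50% is assumed here, with 50% as an extreme. With 1,015 episodes the share of children is 0.70 × s. With 3.36 relapses per child (Poisson) it is 1 − exp(−3.36 s); at s = 20%, for example, 1 − exp(−0.672) = 49%. If all relapses fall on the 70% who relapse (3.36 / 0.70 = 4.8 each), the shares at s = 10/20/30% are 28/46/57%, much the same.

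**Consequence.** Data were simulated with 13 centres, 50 physicians and 597 children:

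dose = mean + 4 × (binary covariate of the episode's prescriber) + centre + prescriber + child + residual

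The assumed variances are 4, 15, 15 and 45. They sum to 79, close to 8.85² = 78.3, but the 8.85 in Section 3.2 is a patient-level SD and fixes neither the total nor the split. Each data set was fitted by REML three ways: crossed, coding (a) and coding (b). There were 200 replicates per setting with 1,015 episodes and 150 with 2,603.

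Coding (a) against the crossed fit:

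| Episodes | s | Children with >1 prescriber | Physician effect, (a) v crossed | Effect too small by | Bias in SEs | Physician variance, (a) v crossed | Variance too low by | 95% coverage |
|---|---|---|---|---|---|---|---|---|
| 1,015 | 10% | 7% | 3.89 v 4.07 | 4.5% | 0.14 | 13.1 v 14.6 | 11% | 95% |
| 1,015 | 20% | 14% | 3.71 v 4.08 | 9% | 0.29 | 11.6 v 14.6 | 20% | 94% |
| 1,015 | 30% | 21% | 3.54 v 4.10 | 14% | 0.45 | 10.3 v 14.4 | 29% | 94% |
| 1,015 | 50% | 35% | 3.05 v 4.06 | 25% | 0.81 | 7.7 v 14.4 | 47% | 86% |
| 2,603 | 10% | 29% | 3.71 v 4.07 | 9% | 0.30 | 11.4 v 14.1 | 19% | 95% |
| 2,603 | 20% | 49% | 3.36 v 4.09 | 18% | 0.63 | 9.1 v 14.4 | 36% | 90% |
| 2,603 | 30% | 64% | 2.90 v 4.06 | 28% | 0.99 | 7.0 v 14.4 | 51% | 78% |
| 2,603 | 50% | 81% | 2.12 v 4.08 | 48% | 1.69 | 3.5 v 14.3 | 76% | 30% |

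The Monte Carlo SE of the difference in effect is 0.016 to 0.055. Some percentages differ by a point from what the rounded means give.

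Coding (b): the physician effect ratio is 1.00 and the variance ratio 0.98 to 1.00. The SE of a patient covariate is below the crossed model's by 1/2/3/4% (1,015 episodes) or 5/9/12/17% (2,603) at s = 10/20/30/50%.

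At s = 0 all three fits are identical.

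**Sensitivity to the variances.** At s = 20% and 1,015 episodes, three other centre/physician/patient/residual splits (4/5/25/45, 4/25/5/45, 10/8/8/53; 100 replicates) give effect ratios of 0.89 to 0.90 and a variance ratio of 0.80. The base case gives 0.91 and 0.80. With 2,603 episodes and the first two splits (40 replicates) the ratios are 0.81 to 0.82 and 0.60 to 0.63. A separate simulation with physician/patient/residual variances 0.20/0.30/0.50 and effect 0.5 (two-episode setting, 30 replicates) gave physician variance 0.182, 0.158 and 0.136 under (a), against 0.196, 0.204 and 0.219 crossed, at s = 10/30/50%. At 50% the residual variance rose from 0.503 to 0.644.

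**The case against.** The strongest reply is that identifier coding in a mixed model is ordinary analysis-plan detail, and that the data forms and variable tables in the appendix, which are not available here, may contain a rule. The damaging coding (a) also requires the analyst to throw away the prescriber link that Section 3.1 creates. If the link is kept, coding (b) leaves physician estimates intact and costs only 1% to 4% on patient standard errors at the planned episode count. With unique study numbers for patients and physicians (Section 3.1), software given separate random intercepts would fit the crossed model whatever the text calls it. The switching rate is unknown, and Section 3.1 speaks of a patient's physician in the singular, so switching may be rare. Even under (a), coverage with 1,015 episodes stays at 94% to 95% up to 30% switching. The 2,603 episodes come from the Objective 1 power inputs, not from the Objective 2 count.

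Much of this stands as a limit on size: the rate is unknown, coding (b) is mild, and the planned episode count with modest switching does little harm to interval coverage. It does not remove the mismatch. The protocol states a model, in three places, that its own linkage contradicts for any child with two prescribers. No coding rule makes strict nesting right for such a child: (a) biases physician effects, and (b) splits one child into several. A package that happens to fit crossed effects would be fitting the model recommended here, not the one written. As for the higher episode count, it follows from the protocol's own relapse rate, whereas 1,015 allows only one relapse per relapsing child.

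**Conclusion.** The concern holds. The nested model and the episode-level prescriber link are inconsistent for children with more than one prescriber, and nothing in the protocol resolves it. The size is conditional on an unstated switching rate and on the coding chosen. Under one-physician coding and 10% to 30% switching, physician variance is 11% to 29% too low with 1,015 episodes and 19% to 51% too low with 2,603; in the latter case coverage for the physician effect falls from 95% to 78%. Split coding affects only the precision of patient effects. The results assume random switching to colleagues in the same centre. The relative attenuation hardly depends on the assumed variance split. This should be corrected, but it is not a fatal flaw, and it vanishes if every child keeps one prescriber.

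**What to change.** In Section 1.0 and in the Analysis plan and sample-size paragraphs of Section 3.3, replace the nesting of patients in physicians by crossed random intercepts for patient and for prescribing physician, within centre. State that physician covariates are those of the episode's prescriber, using the link already defined in Section 3.1. Report the number of children with more than one prescriber.

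The cost is a change of model wording and code, with slightly heavier fitting. No new data are needed, and if no child changes prescriber the result equals that of the planned model.
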